that are specific to PTSD such as struggles with irritability instead of examples of general stressors. 3) The loving-kindness meditation may not be well-received by all patients. After introducing it, ask participants to try it once then suggest that a previously learned, alternative sitting practices (e.g. body scan) can be used by those who don't like it. 4) I found walking meditation to be very helpful. Introduce this before the 4th session. We expect that modifications will adjust specific aspects to make the training more patient-centered and recovery-oriented, while maintaining the core mindfulness pieces.

**C.2.1 Phase 2 Participants:** For the RCT, 60 eligible patients will be enrolled and randomized to PCBMT or EDU. This sample size was chosen because it will require us to recruit 5 participants per month, which is the

Figure 2. Overview of Study Procedures

To illustrate what type of modifications may result from this feedback, possible input could include: 1) Spend less time in discussion and more time in sitting meditation. 2) When discussing how to apply a skill (e.g., non-reactivity to stress) to real life, use examples

rate of recruitment we believe we will need in a subsequent fully-powered RCT (based on a medium intervention effect size and having 3 years to recruit). We have achieved this rate of recruitment in previous studies with similar samples and methods (see B.1., B.4., B.5.).

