**C.2.2. Phase 2 Recruitment:** Recruitment will use a method used by the PI in several other studies, including the ones detailed in B.3. and B.4. Veterans who screen positive on the annual PC-PTSD screen or have active PTSD symptoms will be referred by their primary care or PC-MHI providers. Referrals will be facilitated with a case-finding procedure: study staff will use medical record data to identify patients that may be eligible for the study based on the annual PTSD screening given to all VHA primary care patients (PC-PTSD). For patients who screen positive, we will ask their primary care providers if a recruitment letter can be sent. All referred Veterans will be sent a letter introducing the study and then will be screened over the phone. In our pilot study, PC-MHI providers were a major source of study referrals. Referral from VHA peer support specialists will also be encouraged. Based on our prior recruitment experience (see B.4., B.5.) we are confident we can recruit 5 participants per month to reach 60 enrolled in one year.

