**C.2.3 Phase 2 Procedures:** The baseline session will include informed consent process (Appendix 2) followed by administration of study measures. Participants will be screened for cognitive impairment with the Blessed Orientation Memory and Concentration measure and suicidality with P4 Screener. The P4 Screener assessed past history, plan, probability, and preventive factors and then classifies respondents as minimal, lower or higher risk for suicide. At the baseline assessment, higher risk participants will be connected to VHA Suicide Prevention Services prior to continuing them in the study. In addition to assessing primary outcomes and patient safety, we plan to test the feasibility of measuring concerns that commonly co-occur with PTSD (depression, insomnia, pain, and alcohol/substance misuse) and potential mediators of the relationship between receiving mindfulness training and changes in PTSD symptoms and psychosocial functioning (mindfulness and emotion regulation skills). Pilot data in this area will help us plan for a future full-scale investigation of potential mediators. Post-treatment assessment will occur upon completion of the assigned intervention. We will re-assess participants at two follow-up points: 16 weeks and 24 weeks post-baseline. This will allow the opportunity to test the feasibility of retaining participants over time so that in the full-scale future trial we can test if any changes observed post-treatment are maintained over time. Given that an aim of this line of research is for PCBMT to serve as a bridge to other more intensive PTSD treatments, within the full-scaled trial, data from the 24 week follow-up will also allow the ability to measure changes associated with any new treatments initiated post study treatment. All research assessments will be administered by research staff blinded to randomization outcome. Participants will be reimbursed \$25 per assessment (\$100 total). Randomization will be stratified based on baseline PCL-5 scores (31-40 vs.  $>40$ ) to equate groups at baseline.

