### C.3 Analysis Plan

Aim 1: Gather VHA mental health treatment provider and peer feedback to adapt PCBMT. Co-I [name] will oversee Aim 1 analyses using a Rapid Assessment Process (RAP). This approach is ideal when data needs to be collected and analyzed in one year or less, when only key informants will be interviewed, and when analyses will be deductive. The PI and project coordinator will conduct interviews together with the PI primarily asking questions and the coordinator typing detailed field notes to document responses. A template will be created with a domain name for each interview question (e.g., activating patients, peer roles). The PI, coordinator, and [name] will review the first few sets of field notes collaboratively and summarize content into the domains on the template. After consistency is reached, coders will review the remaining field notes ( $\approx 7$ ) independently. Led by [name], coders will then meet again to analyze summaries and identify suggestions for revisions or aspects seen as helpful that should be maintained within each domain. The PI and Co-Is [name], [name] and [name] will then meet and collectively decide how to modify the protocol. Modifications will only be made if the resulting PCBMT protocol is: 1) feasible to deliver in VHA primary care and 2) stays true to the core mindfulness components. Modifications will be prioritized that are expected to 3) help Veterans develop skills for PTSD symptom management, 4) increase the training’s patient-centeredness, and 5) will affect multiple qualitative domains.

Aim 2: Conduct a pilot RCT (N=60 randomized, n=48 completers) comparing PCBMT to EDU.

**2a.** As this trial will provide us with feasibility information for a larger trial, we will describe the number of participants screened and enrolled per month, proportion of screened participants who are eligible to enroll, completion rates of follow-up assessments, retention rates in study conditions, and the rate and timing of patient drop-out. Recruitment over twelve months will be displayed by plotting the cumulative number of patients enrolled into our study and compared to the anticipated rate of recruitment. Graphs will also be utilized to display rates of intervention and assessment retention at each measurement time. Ninety five percent confidence intervals will be calculated and used in design considerations of a larger trial.

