**2.b.** Participant retention rates in both study interventions will be described with mean, standard deviations and confidence intervals. PCBMT facilitator fidelity will be described quantitatively with the mean number of items endorsed on fidelity checklists. Also items that had lower fidelity will be described to inform future PCBMT training curriculums. Inter-rater reliability will be reported for the 25% of classes rated by an expert observer.

**2.c.** Veteran acceptability (satisfaction, perceived helpfulness, treatment retention): Total CSQ scores and scores on individual CSQ items and Intervention Acceptability items will be described with means, standard deviations and confidence intervals to understand the satisfaction and acceptability in each condition.

**2.d.i.** Patient well-being measured by PTSD severity, depression, health promoting lifestyle behaviors and recovery orientation will be described with means, standard deviations and confidence intervals at each time point by condition. To show central tendency, variation and potential trends over time, means and 95% confidence intervals will be plotted across time for each condition. Additional line plots connecting means across time will overlay the confidence intervals to help illustrate trends. We will also generate an effect size at post-treatment and at each follow-up assessment. Effect sizes will be calculated by dividing the mean difference between conditions by the pooled standard deviation. Then, 95% confidence intervals will be calculated on the effect size by using the non-central t distribution method discussed by Cummings. Graphical methods will be used to plot effects and associated confidence intervals across time which will be used to help design a larger trial. Multi-level modeling will be used to examine group by time effects for each outcome.

**Handling Missing Data.** Multiple Imputation (MI) will be used for missing data. Missing values for variables are predicted using existing values from other variables. These predicted values, called imputes, replace the

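### Randomisation is stratified by baseline PCL-5 but the planned effect-size intervals ignore the stratum: modestly conservative for PCL-5 if allocation is restricted, before any treatment-group clustering

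*Combined protocol and SAP*

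**What the plan says.** C.2.3 Phase 2 Procedures sets the design feature: "Randomization will be stratified based on baseline PCL-5 scores", in two strata (31-40 and above 40), with the stated purpose "to equate groups at baseline". Stratification is mentioned nowhere else. Block size, any other restriction within strata, and the allocation ratio are not given; C.2.1 says only "60 eligible patients will be enrolled and randomized to PCBMT or EDU".

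C.3, 2.d.i defines the analysis of PTSD severity, depression, health-promoting behaviours and recovery orientation: "Effect sizes will be calculated by dividing the mean difference between conditions by the pooled standard deviation". A 95% interval for each effect size then comes from the non-central t distribution. The model-based analysis is one sentence, "Multi-level modeling will be used to examine group by time effects for each outcome", with no covariate list. The missing-data section admits correlated variables to the imputation model but does not name the stratum.

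C.2.1 sets a target of six patients per treatment group, and C.2.5 describes both arms as group-delivered. No analysis mentions the treatment group.

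**The concern.** Balancing the arms on a prognostic stratum removes the between-stratum part of the outcome variance from the arm difference. An interval built on the total pooled SD keeps that part in its standard error. It is then wider than the design requires, and its true coverage exceeds 95%. The usual remedy is to analyse by the factor used to randomise.

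C.3 says the plotted effects and their intervals will help design the larger trial, so their width and calibration matter to the next step. PCL-5 is most exposed, because it is at once the eligibility measure, the stratification factor and an outcome. Adjusting each outcome for its own baseline would not bring the PCL-5 stratum into the analyses of depression, recovery or health behaviours.

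**Working it through.** **Inputs from the documents.** 60 randomised and 48 completers (C.3, Aim 2); two PCL-5 strata (C.2.3); unadjusted d with a non-central t 95% interval (C.3, 2.d.i); groups of about 6 (C.2.1).

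**Assumptions, none given in the documents.** Correlation r between baseline PCL-5 and outcome, 0 to 0.7; share p of patients in the lower stratum, 20% to 50%; permuted blocks of 4 within strata; 1:1 allocation; treatment-group ICC, 0 to 0.10; true d = 0.5. The only hint on effect size is the medium effect mentioned for the future trial.

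**1. The plan's own figures.** 5 per month × 12 = 60, and 48/60 = 0.80, so 20% loss is implied. Both agree with the plan. It states no interval width or coverage to reproduce. At an observed d of 0.5 the planned interval is -0.08 to 1.07 (width 1.15) with 24 per arm, and -0.02 to 1.01 (width 1.03) with 30 per arm.

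**2. Formula, balanced strata and independent patients.** The stratum explains R² = r² × φ(c)² / [p(1-p)] of the outcome variance, where c is the normal quantile of p. Coverage of the unadjusted interval is 2Φ(1.96/√(1-R²)) - 1, and the adjusted-to-unadjusted width ratio is √(1-R²).

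- p = 0.5, r = 0.5: R² = 0.25 × 0.637 = 0.159; ratio 0.917; coverage 96.7%.
- p = 0.5, r = 0.7: R² = 0.49 × 0.637 = 0.312; ratio 0.829; coverage 98.2%.
- Over p = 20% to 50%: 95.2-95.3% at r = 0.2, 96.4-96.7% at r = 0.5, 97.5-98.2% at r = 0.7.

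**3. Simulation with the actual non-central t interval.** 60 randomised, 20% random loss, blocks of 4, p = 30% or 50%, 12,000 trials per setting (8,000 for adjusted coverage). Monte Carlo error is √(0.95 × 0.05/12,000), about 0.2 points.

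| r | Planned coverage | Stratum-adjusted coverage | Width ratio |
|---|---|---|---|
| 0 | 95.0-95.2% | 94.5-95.4% | 1.00 |
| 0.3 | 95.6-95.7% | 95.4% | 0.97-0.98 |
| 0.5 | 96.0-96.6% | 95.1-95.4% | 0.92-0.93 |
| 0.7 | 97.3-97.4% | 94.9-95.2% | 0.83-0.85 |

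On the scale of d with 24 per arm, a width of 1.15 becomes about 1.15 × 0.92 = 1.06 at r = 0.5 and 1.15 × 0.83 = 0.95 at r = 0.7. A separate simulation, with baseline PCL-5 truncated to 31-80 and 69-76% of patients above 40, gave smaller narrowing: about 2%, 6% and 13% at r = 0.3, 0.5 and 0.7. The gain depends on the baseline distribution.

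**4. Simple allocation inside strata (p = 50%).** Planned coverage is 94.4% at r = 0.5 and 94.9% at r = 0.7, so there is no over-coverage. Adjustment still narrows the interval (ratios 0.93 and 0.84).

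**5. Blocks plus clustering in groups of 6 (p = 50%).** Coverage at r = 0.3 / 0.5 / 0.7:

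| ICC | Planned interval | Stratum added, group ignored |
|---|---|---|
| 0.02 | 94.4 / 95.4 / 96.7% | 93.8 / 93.8 / 93.5% |
| 0.05 | 93.2 / 94.1 / 95.7% | 92.5 / 92.6 / 91.7% |
| 0.10 | 90.8 / 91.7 / 93.3% | 90.0 / 89.3 / 88.2% |

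As a rough guide, true variance relative to assumed variance is 1 - R² + (6 - 1) × ICC, so the two omissions cancel when ICC = R²/5. That is 0.159/5 = 0.03 at r = 0.5 and 0.312/5 = 0.06 at r = 0.7. The simulated values cross 95% on either side of these points.

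**The case against.** A reader might infer that the planned intervals are simply too wide and over-cover for every outcome. The documents do not support that, for three reasons, all of which stand.

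- Over-coverage needs restricted allocation within strata, and no restriction is described.
- It needs a prognostic stratum, and no correlation is given. For recovery or lifestyle scores the excess may be too small to matter.
- Patients are treated in groups, and ignoring that lowers coverage. An ICC of a few hundredths is enough to cancel or reverse the excess, and adding the stratum alone could then make calibration worse.

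A reader might also infer that the benefit of stratifying is thrown away, or that these intervals are the pilot's chief product. Neither follows. The stated purpose is baseline balance, and any balance that the allocation achieves does not depend on the analysis. Aim 2 is feasibility, and C.3 also sends the 2.a feasibility intervals into the design of the larger trial.

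Nor is silence exclusion. Baseline is one of the PCL-5 time points and may already sit in the PCL-5 multi-level model, and the imputation guideline could admit baseline PCL-5. Neither route changes the effect-size formula, which is explicit.

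Against the first reason, simple allocation inside strata balances no better than no stratification, so the stated purpose implies some restriction. Against the third, two unmodelled features of unknown size that may partly offset each other do not make a valid 95% interval.

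**Conclusion.** The omission is certain for the effect sizes, whose formula is fixed without the stratum, and is a gap in specification for the multi-level model. Under restricted allocation and independent patients, the planned intervals are modestly conservative: about 96 to 97.5% coverage at an assumed r of 0.5 to 0.7, mainly relevant to PCL-5, with negligible excess at r of 0.3 or below. Under simple allocation, coverage is nominal and only precision is lost. Once treatment-group clustering is allowed for, the net direction cannot be determined from the documents, so a flat claim of over-coverage would be wrong. The correlations, ICC, stratum shares, block size and 1:1 ratio are all assumptions. Severity is low: the intervals are descriptive and no powered test or decision rule depends on them.

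**What to change.** - State the allocation ratio and the method used within strata (for example, permuted blocks).
- At each time point, estimate the arm difference from a model with arm and PCL-5 stratum. Divide it by the unadjusted pooled SD, so that d keeps its meaning, and take the 95% interval from the adjusted standard error.
- Name the stratum as a fixed effect in the multi-level models and include it in the imputation model.
- In the same models, account for treatment group, for example with a random effect or cluster-robust standard errors. Use a small-sample correction, since 60/6 gives only about ten groups. Do not add the stratum without this step.

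The cost is SAP wording and one degree of freedom for the stratum, with no new outcome data. Intervals may widen where clustering is present; that reflects real uncertainty which the current formula omits.

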## **Study Design**

This study will provide the necessary data to apply for a NCCIH R01 focused on a full-scale trial of PC-based Mindfulness Training for Veterans with PTSD. The feasibility study will be conducted in two phases (Figure 2). Phase 1 will collect qualitative feedback on how best to refine and implement PCBMT from VHA providers and peers. Phase 2 will be a feasibility RCT comparing PCBMT to a PTSD psychoeducation group (EDU). Participants will be recruited from two neighboring sites: primary care clinics at the Syracuse and Canandaigua Veterans Affairs Medical Center.

**C.1.1 Phase 1 Participants:** VHA providers and peers will first participate in PCBMT led by certified MBSR instructors (co-Is [name] and [name]). VHA providers experienced in the treatment of PTSD will be encouraged to participate. We are selecting these providers because 1) they will know what skills (e.g. emotional regulation) will be most useful for future participation in evidence-based treatment (EBT) for PTSD and can emphasize those skills when they deliver PCBMT in Phase 2, 2) they have specialized knowledge about Veterans with PTSD, so will provide the research team with quality feedback to refine PCBMT, 3) they will be able to provide EBT for participants who opt to step-up to specialty care following PCBMT, easing the difficult transition from primary to specialty care. This protocol will involve VHA specialty MH providers delivering care in PC, which we believe will increase feasibility because PC-MHI providers often do not have time to deliver treatment outside the brief (i.e., 30 minute), population-based model. Peers will be VHA certified peer support specialists (PSS) currently employed at the Syracuse and Canandaigua VHA. Based on our recent discussion with providers and peers at our recruitment sites, we estimate that 6 providers and 4 peers will be interested and have time to participate in Phase 1. We are not eliciting feedback from Veteran patients on how to adapt PCBMT because we already obtained helpful patient feedback in our pilot study.

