Primary care patients will be recruited and assessed pre and post intervention and at 16 and 24 week follow-up time points. Each quarter, two months will be spent recruiting and 1 month will be used to conduct the intervention groups. Ideal group size is 6 participants. We anticipate running up three consecutive groups (PCBMT and EDU) at each of the two sites. However, our timeline allows for addition groups as needed. To be eligible, participants must be 1) enrolled in primary care at the Syracuse or Canandaigua VAMC and 2) report significant PTSD symptoms (qualifying criterion A traumatic event plus at least a 31 on the PCL-5). Exclusion criteria are minimized because we seek to include any primary care patients with troubling PTSD symptoms that would normally receive treatment in primary care. Patients will be excluded if they demonstrate symptoms that would not allow them to actively participate in PCBMT: 1) gross cognitive impairment ( $>16$  on the Blessed OMC), 2) suicide attempt or desire to commit suicide in the last month (as measured by P4 screener). To allow the study to isolate the effects of the intervention and ensure patient treatment preferences are honored, patients will be excluded if they 3) have received psychotherapy or change in psychiatric medication outside of VHA primary in the last 2 months, or 4) voice a preference to be directly referred to specialty mental health care. Veterans with depression, anxiety disorders, mild TBI, and alcohol/ substance use disorders will not be excluded, because these problems commonly co-occur with PTSD, and individuals with these conditions have previously benefited from mindfulness training. Patients who receive PC-MHI services will not be excluded, as this is part of the usual primary care services that all Veterans can receive.

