#4: Making this practice your own	
 
Yoga followed by body scan
 
Review of past week
 
	
 
Final Reading: “Continue Down the Mindful Path” by [name].
 

 
• Introduce walking meditation
 
• Brief sitting, loving-kindness
 
	
 
• Resources for continued practice.
 

--	---

\* Participants are asked to use the provided 2-minute Chill Out audiorecording at least once daily on all weeks.

EDU is a class designed to provide a supportive environment for learning about PTSD-related issues and to help Veterans determine what recovery strategies will be most helpful for them. Session themes include “Civilian Readjustment and PTSD,” “Trust, Safety, and Healing” and “Treatment Strategies.” This group is currently delivered at the Syracuse site (co-led by a licensed mental health provider and a peer) and a very similar class is delivered at the Canandaigua site. Therefore EDU is an active, PTSD-specific, primary-care based “treatment as usual” comparison group (Appendix 6). These classes were developed locally and no research has been conducted on them. However, psychoeducation for PTSD is often described as an ideal introductory intervention for individuals first entering treatment.

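### Randomisation is stratified by PCL-5 alone, so the split between arms within each site and wave, and to a lesser degree site by arm, is left to chance

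*Combined protocol and SAP*

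**What the plan says.** Section C.2.1 states that "60 eligible patients will be enrolled and randomized to PCBMT or EDU". The Study Design section adds that "Participants will be recruited from two neighboring sites", Syracuse and Canandaigua.

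Delivery is organised by site and wave. C.2.1 says "We anticipate running up three consecutive groups (PCBMT and EDU) at each of the two sites", that "Ideal group size is 6 participants", and that "Each quarter, two months will be spent recruiting and 1 month will be used to conduct the intervention groups". It also allows further groups if needed. Under the PCL-5 entry, C.2.4 says that participants wait until enough people are enrolled to form a group, and that the PCL-5 is repeated if class 1 is not attended within a month of baseline.

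On allocation, C.2.3 says only that "Randomization will be stratified based on baseline PCL-5 scores", with the aim "to equate groups at baseline". The ratio, the blocking method and the timing of randomisation relative to group formation are not given, and neither site nor wave is mentioned. Section C.3 (2.d.i) plans raw standardised mean differences and a multi-level model of group by time, with no site term stated.

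**The concern.** Every wave at every site has to fill two groups at once, one per arm. Stratifying on PCL-5 equalises the arms on severity over the whole trial. It does nothing to equalise them within Syracuse in wave 2, for example, because a PCL-5 stratum runs across both sites and all waves.

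Two things are at stake. The first is feasibility. Sixty patients over 12 groups is 5 per group, already below the ideal of 6, so a lopsided split leaves one arm with a small group or a longer wait. Attendance, retention and acceptability are the outcomes of Aims 2.a to 2.c, and differences between arms could then partly reflect group size or delay. Follow-up is fixed at 16 and 24 weeks from baseline (C.2.3), so a longer wait in one arm also shortens its interval from treatment to follow-up.

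The second is the effect size. Facilitators are drawn from the two sites, and the EDU class run at Syracuse has only a close counterpart elsewhere: "a very similar class is delivered at the Canandaigua site" (C.2.5). If site affects outcome, chance site-by-arm imbalance passes into the unadjusted effect sizes that are meant to inform the larger trial.

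**Working it through.** **Plan's own figure.** C.2.2 gives 5 participants per month for one year: 5 × 12 = 60, which reproduces the target. The pilot has no power calculation to reproduce.

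**Inputs from the documents.** 60 randomised, 2 arms, 2 sites, up to 3 waves per site, and PCL-5 as the only stratifier. This gives 2 × 3 = 6 site-waves, 60/6 = 10 patients in each, and 60/12 = 5 per group.

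**Assumptions not in the documents.** 1:1 allocation; equal sites with exactly 10 patients per site-wave; 60% of patients above 40 on the PCL-5; block sizes as listed below.

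**Unrestricted allocation (exact).** In one site-wave the PCBMT count is Binomial(10, 0.5).
- 7:3 or worse: 2 × (120 + 45 + 10 + 1)/1024 = 0.344. At least one of six: 1 − (1 − 0.344)^6 = 0.92.
- 8:2 or worse: 2 × (45 + 10 + 1)/1024 = 0.109. At least one of six: 1 − (1 − 0.109)^6 = 0.50.
- 20:10 or worse at a given site, Binomial(30, 0.5): 0.099.

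**Blocked within PCL-5 strata (simulation; blocks of 2, of 4, or mixed 4 and 6).**

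| Event | Blocked within PCL-5 | Unrestricted |
|---|---|---|
| 7:3 or worse, a given site-wave | about 20-22% | 34% |
| 7:3 or worse, at least one of six | about 58-67% | 92% |
| 8:2 or worse, at least one of six | about 11-17% | 50% |
| 20:10 or worse at a given site | about 2% | 10% |

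The 2% agrees with the exact hypergeometric value when the arms are 30:30 overall (0.019). With blocks of 4, taking 40% or 80% of patients above 40 on the PCL-5 gives 65% and 62% for the second row, so that assumption matters little.

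**Site by arm.** With PCL-5 as the only stratifier, the two sites split 17:13 and 13:17 or worse in 37-41% of trials, and 18:12 and 12:18 or worse in 16-19%. Blocking within PCL-5 strata does not lower these figures.

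**Size of the confounding.** A split of 18:12 and 12:18 means site shares of 18/30 = 60% and 12/30 = 40%, a 20-point gap. If the sites differed by an assumed 0.5 SD, the effect size would shift by 0.20 × 0.5 = 0.10. Its standard error is about √(2/30) = 0.26 with 30 per arm.

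**After stratifying by site and PCL-5.** Sites' PCBMT counts differing by 4 or more become very rare (about 0% with blocks of 4). At least one 7:3 or worse site-wave remains in about 12% of trials with blocks of 2, 27% with blocks of 4, and 37% with mixed blocks of 4 and 6.

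**If site intake varies by chance** (equal expected shares, three waves), at least one group of 3 or fewer occurs in 94% of trials with PCL-5-only blocks of 4, in 84% with site and PCL-5 blocks of 4, and in 60% with blocks of 2 inside each site-wave. Part of the small-group risk therefore comes from intake and cannot be removed by randomisation.

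**The case against.** The strongest reply is that the plan does not describe coin-flip allocation. Stratifying to equalise the arms normally goes with blocking, and under blocking the chances are clearly lower. That stands: 92%, 50% and 10% are an upper bound, and the blocked figures should be read first. Even so, at least one 7:3 or worse site-wave is more likely than not under every PCL-5-only scheme tried.

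Second, the timing of randomisation is not stated. If each site's cohort were randomised together in a balanced batch once a group could be formed, most of the problem would disappear. That is true, but the documents do not say it is done.

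Third, a reader might infer that groups will be too small to run. The documents do not support this: C.2.1 sets no minimum size, calls 6 ideal, and allows further groups, while C.2.4 already provides for waiting.

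Fourth, a reader might infer that site is seriously confounded with arm. That is not supported either. The two EDU classes are described as very similar, C.2.5 gives both arms a common structure, and chance imbalance adds variance rather than bias in expectation.

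Finally, this is a pilot whose effect sizes carry confidence intervals. That limits the harm to the effect sizes but not to the feasibility measures, which are its purpose.

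**Conclusion.** The concern holds as a cheap design improvement and is not a fatal flaw. Stratifying on PCL-5 alone leaves the arm split within each site and wave to chance. The likely size is a 58-67% chance of at least one 7:3 or worse site-wave under blocking, up to 92% without it. The more extreme 8:2 split has 11-17% under blocking and 50% without. These figures rest on 1:1 allocation and 10 patients per site-wave.

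The consequence to emphasise is uneven group size and waiting time, because these bear on attendance and retention. Site-by-arm imbalance is a secondary matter: a 20-point gap arises in about one trial in six, and at an assumed 0.5 SD site difference it moves the effect size by well under half a standard error (0.10/0.26 = 0.38). The documents support neither a prediction of unworkable groups nor one of strong site confounding.

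**What to change.** In C.2.3, state: *Allocation will be 1:1, stratified by site (Syracuse, Canandaigua) and baseline PCL-5 (31-40, >40), using small permuted blocks of varying size concealed from recruiters.* Say also when randomisation takes place relative to group formation.

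In C.3 (2.d.i), include site and PCL-5 stratum as fixed effects in the multi-level model. The raw standardised differences are not adjusted by that step, so for them the protection comes from the stratification.

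The cost is a revised allocation list before enrolment and two model terms. There are two downsides. Small blocks are slightly more predictable, which varying and concealing the sizes limits. And wave-level imbalance is reduced, not removed: 12-37% of trials keep a 7:3 or worse site-wave, with smaller blocks at the lower end.

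Randomising each site's wave cohort in a balanced batch would reduce this further. Crossing site, wave and PCL-5 as ordinary strata would give 60/12 = 5 patients per cell on average, so that route would need very small blocks or minimisation.
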